Esophageal food impaction is a relatively common illness, estimated to occur at a rate of 13 episodes per 100,000 people per year, mostly men, and usually attributed to swallowed meat bolus. Current standard of care for patients presenting to an Emergency Department with presumed esophageal food impaction includes trial of medical therapy, usually glucagon but sometimes effervescent liquid, sublingual or intravenous nitroglycerin, or benzodiazepines, with a backup of endoscopy for definitive mechanical removal of the food bolus. Glucagon has significant uncomfortable side effects, chiefly nausea and vomiting. The medical interventions mentioned above have not been shown to have significant efficacy; endoscopy is frequently performed after failure of medical management. There is significant risk associated with endoscopy, including the risks of anesthesia as well as with the physical procedure itself. Endoscopy also results in a prolonged hospital stay due to the time required for the procedure, as well as from anesthesia recovery. The ideal treatment would be a safe, inexpensive, quickly effective medical intervention without significant side effects that could be administered without sedation or extensive monitoring. Oral nitroglycerin solution might just be that intervention.

No published trials or case reports using oral nitroglycerin solution for esophageal food impaction were found. Two recent unpublished cases using oral nitroglycerin solution were remarkably and rapidly effective (within 2 minutes) in relieving esophageal food impaction symptoms. The currently proposed study would provide preliminary data which may motivate a larger controlled study.

4. Approach

a. Study design

Prospective, unblinded, single-arm cohort of patients presenting to the Emergency Department with presentation consistent with esophageal food impaction.

b. Population

i. Inclusion/Exclusion Criteria [See Human Subjects items to be moved here]

1. Inclusion Criteria:

- a. Over the age of 18 years
- b. Presentation consistent with esophageal food impaction
- c. Ability to swallow a small volume of liquid.

2. Exclusion Criteria:

- a. Intractable vomiting
- b. Hemodynamic instability or SBP <100 mmHg
- c. Concern for or evidence of significant airway compromise
- d. Concern for or evidence of esophageal perforation,
- e. Concern for or evidence of coronary ischemia
- f. Presentation > 12 hours since onset.

ii. Sample size

1. Convenience sample of 20 patients.

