1. Study subjects who meet all of the inclusion criteria and none of the exclusion criteria will be approached for consent by study staff prior to enrollment. If an eligible patient is not being cared for by the PI or a Co-I, study staff must approach the patient's provider to determine if it is appropriate to proceed with the consent process. If additional testing needs to be done to see whether a patient meets criteria for entry into the study, the PI, a Co-I, or staff will need to consent the patient first. If the preparation activity confirms a patient is a possible subject, PI/research staff approaches the patient to begin the consent process.

iv. Data sources

1. Study subjects will be interviewed prior to treatment and again after treatment. Medical records from the visit will be collected.
2. Please see attached chart titled "Data Collection Form" describing the variable name, data source, purpose, and measurement scale in the initial application submission

v. Process steps for data acquisition

1. The study subject's demographical, medical, and surgical history, and symptom data will be initially collected from medical record and interview by investigators and/or research assistants during the Emergency Department visit. First at enrollment, then after each administration of study medication. Data will be collected by study investigators and/or research assistants. Data collected includes:
 - Medical record number (MRN), Age, Gender, Visit date, Allergies, Blood pressure, Presenting complaint / HPI, Symptoms throughout the ED visit, medical history, surgical history, time and dose of medications administered
2. The patient's ED provider will be asked for appropriateness for inclusion in the study (yes to any answer will count as an exclusion). They will be asked:
 - a. Is symptoms onset more than 12 hours ago?
 - b. Is there concern for airway obstruction?
 - c. Is there concern for esophageal perforation?
 - d. Is there concern for coronary ischemia?
 - e. Are there any other concerns about including this patient in the study?
3. After discharge of the patient (either from the ED or after admission), their medical record will be accessed for data abstraction by investigators and/or research assistants. The following data will be collected:
 - a. Disposition from the ED
 - b. Length of stay
 - c. Procedures performed during the visit
 - d. Medications given during the visit
 - e. Condition at discharge

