4. A single follow-up phone call will be made by investigators and/or research assistants between 4-7 days after discharge to obtain:
 - a. Symptoms at discharge
 - b. Symptoms currently
 - c. Any other treatment required since hospital discharge
 - d. Satisfaction survey

d. *Intervention, treatments*

- i. Up to 3 administrations of 0.4mg sublingual nitroglycerin tablets, dissolved in 10mL tap water, given orally in a single swallow. Each administration is separated by at least 5 minutes, and only if systolic blood pressure > 100 mmHg. The patients then have to pass a swallow test before discharge. The passing of the swallow test will indicate a treatment success. Treatment failure is

defined as lack of symptom resolution 10 minutes after the last dose of nitroglycerin OR inability to tolerate administration OR intolerable side effects.

e. Outcomes/endpoint and other variable definitions, and instruments used

- i. Primary Endpoint is the patient is able to swallow without difficulty within 10 minutes after nitroglycerin administration.
- ii. Secondary endpoint is adverse events during the hospital stay.

f. Statistical analysis plan

- i. Descriptive statistics will be used to summarize the study sample and to evaluate efficacy of the study intervention and frequency of side effects. Specifically, we will first calculate summary statistics (mean \pm standard deviation, frequency counts and percentages) for relevant patient factors (demographics, etc.) at the time of presentation to the ED. We will then calculate the proportion of study patients who achieve resolution of food impaction, with a corresponding 95% confidence interval. Similarly, we will also report frequencies of adverse events, overall and by type of adverse event, along with appropriate measures of variance (including headache frequency and change in blood pressure). Finally we will report outcome statistics (frequency counts and percentages) for repeat symptoms subsequent to the hospital visit (from follow up phone call). Symptom data from follow-up phone call will be used, non-statistically, to identify possible delayed complications of oral nitroglycerin use.

g. Power analysis or statement of precision

- i. No formal hypothesis testing will be pursued, thus we have not conducted a power analysis.. Given the proposed sample size ($n=20$), and projecting 90% success in resolving food impaction (18/20), we anticipate a 95% confidence interval of (68.3%, 98.8%).

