h. Strengths and limitations

- i. Strengths
 1. New, promising medical intervention for esophageal food impaction with a strong theoretical likelihood of success.
- ii. Weaknesses
 1. Being a pilot study, further research will need to be undertaken to fully assess the safety and efficacy of the proposed intervention. We will not enroll a comparison group, statistical precision will be limited due to small sample size, and all results will be descriptive (no control for covariates).

5. Setting/Environment/Organizational feasibility

- a. This study is easily achievable, as the study cohort regularly presents to the Emergency Department, the study medication is inexpensive, universally available, and very easily administered.
- b. Research assistants are available 24/7/365 to help with enrollment and data collection.

6. Risks and Benefits

- a. The risks to study subjects are minimal. As with any medication, there is a risk of allergic reaction. Nitroglycerin causes vasodilation and has been associated with modest reduction in blood pressure, however this medication has been safely used for many years. The theoretical systemic absorption of oral nitroglycerin solution is slower than sublingual, and since its half-life is very short, systemic effects may very well be less prominent than with sublingual or intravenous administration.
- b. The benefits to study subjects include potentially rapid reversal of symptoms and food impaction with minimal delay or side effects, avoidance of admission and endoscopy, and avoidance of use of glucagon.

7. Data Confidentiality and Privacy

- a. This study is being conducted in accordance with the ethical principles that are consistent with the ICH and Good Clinical Practice. Once a patient is identified, they are assigned a unique identification number that is assigned to the patient for the duration of the study. The master database linking the patient MRN with the unique identification number is stored on a password-protected, secure share drive housed in the Critical Care Research Center. The CCRC is a locked office with limited accessibility. All

CCRC research staff have EPIC access via a unique user name and password that is monitored by IS&T Security. All research staff are fully trained on the elements of patient privacy, HIPAA and confidentiality.

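### Investigators who may also be treating the patient can collect the open-label symptom data that help decide success, and nobody is named to score the swallow test, although research assistants are available at all hours.

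*Combined protocol and SAP*

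**What the plan says.** All references are to the combined protocol and SAP.

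- **Design (4.a).** "Prospective, unblinded, single-arm cohort of patients presenting to the Emergency Department". There is no comparator.
- **Collection in the emergency department (4.c.v.1).** The timing is "First at enrollment, then after each administration of study medication", and the collectors are given as "Data will be collected by study investigators and/or research assistants". The list of items includes symptoms during the visit, blood pressure and medications. It does not include the swallow test.
- **Follow-up call (4.c.v.4).** "A single follow-up phone call will be made by investigators and/or research assistants between 4-7 days after discharge to obtain" symptoms at discharge and now, further treatment, and a satisfaction survey.
- **Treating clinician (4.c.iii).** The consent step makes a special provision that begins "If an eligible patient is not being cared for by the PI or a Co-I". The investigator may therefore be the treating clinician.
- **Outcome (Section 2, 4.d, 4.e).** Aim 1 judges success by both symptom resolution and ability to swallow. Section 4.d counts a passed swallow test as success. It counts as failure unresolved symptoms 10 minutes after the last dose, inability to take the drug, or intolerable side effects. Section 4.e sets the primary endpoint as swallowing without difficulty within 10 minutes. No assessor, test material or pass rule is given for the swallow test.
- **Staffing (5.b).** "Research assistants are available 24/7/365 to help with enrollment and data collection". Section 4.c.ii adds that research staff are on site, with on-call cover around the clock.
- **Limitations (4.h).** The list covers the absence of a comparison group, limited precision and lack of covariate control. It does not mention unblinded assessment or assessment by investigators.

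**The concern.** Whether swallowing is free of difficulty, whether symptoms have resolved and whether side effects are intolerable are all matters of judgement. Nothing in the text stops one person from treating the patient, asking about symptoms, judging the outcome and making the later call.

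With no control arm, lenient scoring is not offset by the same leniency in a comparator. Several adverse events named in Aim 2, such as headache, lightheadedness and pain, depend on what the patient reports, and so on who asks and how. Patients may speak less freely to the clinician who treated them.

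The protocol is also openly hopeful. It lists as its strength "New, promising medical intervention for esophageal food impaction with a strong theoretical likelihood of success", and 4.g projects 90% success. This does not show that anyone would score leniently, but it is a reason to keep outcome recording apart from the investigators where that costs little. The success proportion is the main output of the study and, by Section 3, may prompt a larger controlled trial.

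**Working it through.** **1. Which data decide the outcome, and who may collect them**

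| Item | Use | Who may collect it, by the text |
|---|---|---|
| Symptoms after each dose (4.c.v.1) | Failure rule in 4.d; Aim 1 | Investigator or research assistant |
| Swallow test (4.d) | Success rule | Not stated |
| Patient-reported adverse events in hospital (Aim 2, 4.e) | Secondary endpoint; the intolerable-side-effects limb of failure | Symptoms: investigator or research assistant; no separate rule for adverse events |
| Call 4 to 7 days after discharge (4.c.v.4) | Repeat symptoms, possible delayed complications (4.f); satisfaction | Investigator or research assistant |

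The first row shows that the sentence in 4.c.v.1 reaches data that help decide success or failure. The second shows that investigator scoring of the swallow test is left open by silence and is not stated. The last shows that the call comes too late to change the 10-minute primary endpoint. It also comes after the hospital stay to which 4.e confines the adverse event endpoint.

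**2. The plan's own interval**

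Inputs from 4.g: n = 20, x = 18, 95% confidence. The exact (Clopper-Pearson) limits are:

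- lower = 2.5% quantile of Beta(x, n − x + 1) = Beta(18, 3): 68.3%
- upper = 97.5% quantile of Beta(x + 1, n − x) = Beta(19, 2): 98.8%

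This matches the stated interval. No figure in the plan is wrong, and changing the assessor leaves n and the planned interval as they are.

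**3. Sensitivity to scoring error (illustration)**

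One patient is 1/20 = 5 percentage points. The documents give no error rate, so the counts below are assumptions. Suppose 18/20 is observed and k of those successes were really failures:

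| k (assumed) | True count | True rate | Exact 95% CI |
|---|---|---|---|
| 0 | 18/20 | 90% | 68.3 to 98.8 |
| 1 | 17/20 | 85% | 62.1 to 96.8 |
| 2 | 16/20 | 80% | 56.3 to 94.3 |
| 3 | 15/20 | 75% | 50.9 to 91.3 |

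The same can be put as a rate. If the true success rate is p, a share f of true failures is scored as success, and no true success is missed, the expected observed rate is p + (1 − p)f.

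- p = 0.70: f = 0.10 gives 0.70 + 0.30 × 0.10 = 73%; f = 0.30 gives 0.70 + 0.30 × 0.30 = 79%.
- p = 0.90: f = 0.10 gives 0.90 + 0.10 × 0.10 = 91%; f = 0.30 gives 0.90 + 0.10 × 0.30 = 93%.

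The effect is small if the drug works as well as projected and larger if it does not. The confidence interval describes sampling error only and does not cover this error.

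**The case against.** **The collection sentence does not name the swallow test.** This stands. A reader might infer that the protocol assigns scoring of the primary endpoint to investigators; it does not. What remains is that investigators may collect the symptom data, which enter the failure rule, and that the swallow test has no named assessor. The data collection form cited in 4.c.iv is not reproduced and may say more, but the protocol text sets no separation of roles.

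**The call cannot bias the success rate.** This also stands. It can affect only the reports of repeat symptoms, delayed complications and satisfaction.

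**A research assistant knows the treatment too and belongs to the same team.** True. The change lowers the personal stake of the assessor; it does not create a blinded assessment. Only that part of the bias is avoidable.

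**Availability is not the same as presence.** Some cover is on call, and the outcome is judged minutes after a dose, so an assistant may not always be at the bedside. This calls for a documented fallback and does not defeat the proposal.

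**There are partial checks.** Record abstraction in 4.c.v.3 captures procedures, medications and disposition, so a failure scored as success that went on to endoscopy would be visible. Blood pressure is measured. These checks limit gross error. They do not settle borderline symptom judgements.

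**Little turns on it.** No hypothesis test is planned, and the study is a descriptive pilot. That limits the importance of the point, but the success proportion is still the figure that readers will carry forward.

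**Conclusion.** The point holds as a low-cost improvement, of modest weight. In an open, uncontrolled study, the protocol lets investigators who may be treating the patient collect symptom data that help decide the outcome, and it leaves the swallow-test assessor unnamed. Staff who could do this at arm's length are described as available at all hours.

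A reader might go further and conclude that the success rate will be biased, or that the projection of 90% reflects lenient scoring. The documents support neither. They show an opening for bias, and the projection serves only to state precision.

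The size is 5 percentage points per misclassified patient. How many patients would be misclassified is unknown; the counts of one to three and the shares of 10% to 30% are assumptions, and the rate formula further assumes that no true success is scored as a failure. The consequence is for the credibility of a descriptive estimate and of the patient-reported adverse event counts.

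**What to change.** Change the wording in four places.

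- **4.c.v.1 and 4.d:** state that the research recording of symptom resolution, the swallow test result and the adverse event questions is done by an available research assistant not involved in the patient's treatment, using a fixed script. State the pass rule for the swallow test before enrolment starts; its content is for the study team to set.
- **4.c.v.4:** assign the follow-up call to such an assistant, also with a fixed script.
- **4.c.v.1, with reporting in 4.f:** where an investigator has to score a patient, record this and report the number of such patients.
- **4.h:** list unblinded outcome assessment as a limitation.

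The change concerns research recording only; the treating team's clinical decisions, including discharge, are unchanged.

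**Cost:** protocol wording, a short script and one extra field on the data form. By the protocol's own account the staff are in place, and sample size and analysis method do not change. The downsides are an occasional investigator fallback when the assistant is only on call, and an assessor who still knows that the drug was given, so bias is reduced and not removed.

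### Three different success wordings, none requiring relief that lasts to discharge without other treatment, leave the primary proportion undefined for a patient who re-obstructs during the visit

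*Combined protocol and SAP*

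**What the plan says.** Success is described in three places.

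- **4.e.i, the primary endpoint:** "Primary Endpoint is the patient is able to swallow without difficulty within 10 minutes after nitroglycerin administration". It does not say that the ability must persist.
- **4.d, the intervention section:** "The patients then have to pass a swallow test before discharge", followed at once by "The passing of the swallow test will indicate a treatment success". Neither the time nor the content of the test is given, and nothing excludes a test passed after another treatment. The rule for failure in the same section reads: "defined as lack of symptom resolution 10 minutes after the last dose of nitroglycerin OR inability to tolerate administration OR intolerable side effects". Return of obstruction is not listed.
- **4.f, the analysis plan:** the efficacy result is the proportion of patients whose impaction resolves, with a 95% confidence interval. No time point is attached, and there is no link to 4.d or 4.e.i.

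Section 4.f plans a recurrence summary only for symptoms after the hospital visit, taken from the follow-up call. Section 4.c.v does collect in-visit information: symptoms during the ED stay, "Procedures performed during the visit", medications given, and the patient's state at discharge. None of it is tied to the success definition.

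**The concern.** Aim 1 asks how often the solution relieves the impaction. A patient who improves at 10 minutes, obstructs again an hour later and has the bolus removed by other means has not been relieved in the sense that matters. That patient also does not gain the avoidance of endoscopy that section 6.b lists as a benefit. If the primary proportion includes such patients, it overstates what the drug achieved.

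The study has one arm and no hypothesis test, so this proportion is its main efficacy result. Section 3 says the data may motivate a larger controlled study. The in-visit relapse also falls into a gap: it comes after the 10-minute assessment and before the period covered by the phone-call summary.

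**Working it through.** **Step 1: the plan's own figure.** Section 4.g gives 68.3% to 98.8% for 18 successes in 20. The exact (Clopper-Pearson) limits for x successes in n are

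- lower = 2.5% quantile of Beta(x, n − x + 1)
- upper = 97.5% quantile of Beta(x + 1, n − x)

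With x = 18 and n = 20, these are the 2.5% quantile of Beta(18, 3) and the 97.5% quantile of Beta(19, 2): 68.3% and 98.8%. The stated interval is reproduced and is not in dispute.

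**Step 2: apply each wording to four kinds of patient.** All are assumed to tolerate dosing, without intolerable side effects, and to swallow well with symptoms resolved 10 minutes after the last dose.

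| Course after 10 minutes | 4.e.i | 4.d success | 4.d failure | 4.f |
|---|---|---|---|---|
| Stays well, passes test | met | met | no | resolved |
| Re-obstructs, bolus removed by other means, then passes test | met | met | no | can be read as resolved |
| Passes test early, then re-obstructs | met | met | no | unclear |
| Re-obstructs and is tested while obstructed | met | not met at that test | no | not naturally resolved |

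The second row is the clearest problem: 4.e.i and 4.d success are both met, and no failure criterion applies. The fourth row shows the wordings disagreeing. Because a pass is required before discharge, a fourth-row patient who is then treated by other means and retested moves into the second row.

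**Step 3: size.** One patient in 20 is 1/20 = 5 percentage points. The documents give no rate of early return, so the counts below are assumptions. Each row takes that many patients out of the 18 projected successes and recounts them as failures.

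| Assumed early returns | Sustained success | Exact 95% CI |
|---|---|---|
| 0 | 18/20 = 90% | 68.3 to 98.8 |
| 1 | 17/20 = 85% | 62.1 to 96.8 |
| 2 | 16/20 = 80% | 56.3 to 94.3 |
| 3 | 15/20 = 75% | 50.9 to 91.3 |

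**The case against.** The strongest reply is that 4.d makes the swallow test an explicit success criterion and not merely a discharge condition. A patient who is obstructed when tested does not pass, and on that wording is not a success. Section 4.f speaks of the impaction resolving, which a patient needing mechanical removal does not naturally fit. So a reader might infer that the plan definitely scores every transient responder as a success and that its estimate is therefore biased upward. The documents do not support that: it would follow only if 4.e.i were known to override 4.d and 4.f, and no such ranking is stated. This part of the reply stands.

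A reader might also take the remark in section 6.a as evidence that esophageal relief wears off. The full clause is "since its half-life is very short, systemic effects may very well be less prominent than with sublingual or intravenous administration". It is a safety argument about systemic exposure and says nothing about how long swallowing stays improved. This part stands too.

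It is also fair that the study is exploratory, that its limited precision is acknowledged, and that the counts in the illustration are chosen.

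The swallow test does not close the gap, however. It has no stated time, so an early pass can precede a relapse. It is not restricted to patients without other treatment, so a late pass can follow bolus removal.

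**Conclusion.** The concern holds as a gap in definition. The plan has three success wordings, does not say which one is analysed, and does not say how a return of obstruction before discharge is classified. Under 4.e.i and 4.d as written, a patient who responds, relapses, is treated by other means and then passes the test is a success with no failure criterion met. Section 4.f does not clearly exclude that patient.

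The effect is 5 points per patient, upward, if such patients occur and are counted. How many would occur is unknown, and the illustration of 90% falling to 80% rests on an assumed two. The issue should be settled before the data are analysed, because with 20 patients a few classification decisions can move the headline result materially.

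**What to change.** Reconcile 4.d, 4.e.i and 4.f into one primary success definition for the analysis, and have 4.f and 4.g refer to it. A patient counts as a success if all of the following hold:

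1. swallowing without difficulty within the 10-minute window;
2. no recorded return of impaction symptoms before discharge;
3. no other impaction treatment or bolus removal during the visit;
4. a passed pre-discharge swallow test.

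Report the proportion meeting item 1 alone, with its exact interval, next to the primary result, so that early but unsustained responses can be seen. This is a rule for classifying outcomes and does not change how any patient is managed.

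The sources are already planned: ED symptom data, procedure and medication records, state at discharge, and the swallow test. Two limits should be written down. The time of the swallow test should be recorded, since the protocol does not state it and an early pass says little about relief lasting to discharge. For admitted patients, symptom return after leaving the ED is captured only indirectly, through procedures, medications, state at discharge and recall at the follow-up call.

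The cost is mainly wording, with no added patients or visits. The downside is that the headline success rate may be lower.

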Official Title: Esophageal Food Impaction (ONEFIT)

NCT#: NCT03305848

Study Protocol and Statistical Analysis Plan

Document Date: July 26, 2017

Participant Contact Project Narrative

1. Summary

A piece of food stuck in the esophagus (the tube connecting the mouth to the stomach) is a relatively common occurrence, estimated at a rate of 13 episodes per 100,000 people per year, mostly men, and usually attributed to swallowed meat. The current standard of care for patients presenting to an Emergency Department with this problem includes a trial of medication, usually glucagon but sometimes a carbonated beverage, an injection of nitroglycerin, or benzodiazepines. The medical interventions mentioned above have not been shown to be significantly effective and have unwanted side effects; glucagon is known to cause nausea and vomiting and benzodiazepines can cause sedation and depressed breathing. If the medication fails to relieve the problem, the patient may require a procedure called endoscopy, where a video scope and retrieval tool are inserted into the esophagus to remove the piece of food. There is significant risk associated with endoscopy, including the risks of anesthesia as well as with the physical procedure itself. Endoscopy also results in a prolonged hospital stay due to the time required for the procedure, as well as from anesthesia recovery. The ideal treatment would be a safe, inexpensive, quickly effective medication without significant side effects that could be administered without sedation or extensive monitoring. Oral nitroglycerin solution might just be that intervention.

2. Study aims

Obtain exploratory data on the safety and efficacy of oral nitroglycerin solution for the treatment of esophageal food impaction in a cohort of patients presenting to the ED with presumed esophageal food impaction.

Aim 1: Efficacy. We will determine the success rate of oral nitroglycerin solution in relieving the food impaction by assessing the resolution of symptoms and the ability of the patient to swallow.

Aim 2: Safety. We will calculate the frequency of adverse events from this medical intervention. We are mainly concerned with hypotension, lightheadedness, headache, allergic reaction, dyspnea, vomiting, and pain.

3. Background, Rationale, Significance

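### Aim 2 asks for adverse events due to nitroglycerin, but the only counting rule takes all events of the hospital stay, with no split at rescue and no rule for symptoms present before dosing

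*Combined protocol and SAP*

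**What the plan says.** **Target.** Section 2, Aim 2: "We will calculate the frequency of adverse events from this medical intervention". The events of interest are then listed: "We are mainly concerned with hypotension, lightheadedness, headache, allergic reaction, dyspnea, vomiting, and pain". The opening of section 4.f likewise says that the descriptive statistics will address side effects.

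**Counting rule.** Section 4.e.ii: "Secondary endpoint is adverse events during the hospital stay". Section 4.f adds that frequencies will be given in total and for each type, with measures of variance. It names headache and change in blood pressure as examples.

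**What else can happen in the stay.** Section 3 says of the usual drug: "Glucagon has significant uncomfortable side effects, chiefly nausea and vomiting". It also says that "endoscopy is frequently performed after failure of medical management", and adds: "There is significant risk associated with endoscopy, including the risks of anesthesia as well as with the physical procedure itself".

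**State before dosing.** Of the symptoms on the Aim 2 list, the exclusion criteria in section 4.b.i name only "Intractable vomiting"; low systolic pressure is excluded separately. Section 4.c.iv says: "Study subjects will be interviewed prior to treatment and again after treatment". Section 4.c.v collects symptoms at enrollment and after each dose, the times and doses of medications and, from the record, the procedures performed.

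**The concern.** The target is causal (events due to the study drug), while the count is defined by a time window alone. Nothing in 4.e.ii or 4.f starts the count at the first dose, divides it at rescue, or compares a symptom with its pre-dose state. Blood pressure, analysed as change, is the one exception.

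Two kinds of event can therefore enter the frequency without being due to nitroglycerin:

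- **Events after rescue.** A patient who fails nitroglycerin, receives glucagon and then vomits has an adverse event during the stay. So does a patient with a complication of endoscopy or anesthesia.
- **Symptoms already present.** Vomiting short of intractable, pain and dyspnea may be there at the pre-dose interview. The plan does not say whether an unchanged symptom counts.

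With no comparison group, the analysis cannot separate these later. Two analysts following the plan could report different vomiting or pain frequencies from the same 20 patients. Safety is one of two aims and the only secondary endpoint, and section 3 offers the results as preliminary data that may motivate a controlled study.

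**Working it through.** **1. The plan's own figure.** Section 4.g gives 68.3% to 98.8% for 18/20. The exact (Clopper-Pearson) limits are the 2.5% quantile of Beta(18, 3) and the 97.5% quantile of Beta(19, 2): 68.3% and 98.8%. They match. Wilson (69.9% to 97.2%) and Wald (76.9% to 100%) do not. The figure is not in dispute; the check shows which interval method the plan uses.

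**2. The rule applied to three hypothetical patients.**

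| Patient | Due to nitroglycerin (Aim 2)? | Counted under 4.e.ii? |
|---|---|---|
| First vomits after the first dose, before any other treatment | Plausibly | Yes |
| Fails, receives glucagon, then first vomits | Not clearly; section 3 gives glucagon as a cause | Yes |
| Vomiting before dosing, not intractable, unchanged afterwards | No | Not settled by the text |

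The second and third rows are where the count and the aim part company.

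**3. Which event types are affected.** The baseline problem is limited to vomiting, pain and dyspnea. Low systolic pressure is an exclusion and blood pressure is analysed as change. The documents do not present headache, lightheadedness or allergic reaction as impaction symptoms.

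**4. Size.** Inputs: n = 20 (section 4.b.ii) and projected success 18/20 (section 4.g).

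- One wrongly attributed patient adds 1/20 = 5 points for that event type.
- Projected failures are 20 − 18 = 2. If only failures go on to rescue (an assumption), rescue adds at most 2 patients per type: 2/20 = 10 points. In general, k failures give a ceiling of k/20.
- The ceiling requires that both failures are rescued, both have the event afterwards, both events are recorded, and neither patient was already counted for that type. Section 4.d counts inability to tolerate the drug as failure, so some failures may already be counted. The range is 0 to 2 patients.
- For pre-dose symptoms, b affected patients add up to b/20. The documents give no prevalence, so no value of b is claimed.

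Exact 95% intervals show the scale, using hypothetical counts due to the drug:

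| Due to drug | After adding | Frequency and interval |
|---|---|---|
| 0/20 | none | 0% (0 to 16.8%) |
| 0/20 | 1 patient | 5% (0.1 to 24.9%) |
| 0/20 | 2 patients | 10% (1.2 to 31.7%) |
| 2/20 | none | 10% (1.2 to 31.7%) |
| 2/20 | 1 patient | 15% (3.2 to 37.9%) |
| 2/20 | 2 patients | 20% (5.7 to 43.7%) |

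These are illustrations, not estimates.

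**The case against.** **Aim and endpoint can be read together.** On this reading Aim 2 and the side-effects wording of 4.f give the target, and 4.e.ii gives only the observation period. Counting an unchanged presenting symptom would then go against the aim. This stands in part: the authors plainly intend drug attribution. But no passage turns the intention into a rule, and the window that is stated answers a wider question.

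**An all-events count is a legitimate choice.** For a 20-patient descriptive pilot, a whole-stay total is inclusive and does not depend on judging cause. This stands, and is why the total should be kept. It does not supply the Aim 2 quantity.

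**The numerical effect is small and unsourced.** At the projected success rate no more than two patients per event type are at issue, and the intervals in the table overlap heavily. This stands. A reader might infer that the nitroglycerin rate will be inflated by a predictable amount; the documents give no rate from which to predict one. Incomplete recording of later events would shrink the effect. Structured symptom collection follows the doses and the ED visit, with later information coming from the record and the follow-up call.

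**The form may already cover it.** The Data Collection Form cited in section 4.c.iv is not in the documents and may hold onset or relatedness items. A reader might infer that the needed data are not collected. That cannot be concluded: pre-dose and post-dose symptoms and medication times are listed. What can be said is that 4.e.ii and 4.f use no such item.

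**The limits are disclosed.** Section 4.h admits the lack of a comparison group and the low precision. It does not say how events are to be assigned.

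**Conclusion.** The concern holds as a gap between the safety aim and the only rule for counting events. As written, the frequency can include events after rescue and symptoms that preceded the drug. Each patient so counted moves a type-specific frequency by 5 points. If only failures are rescued and success is 18/20, rescue can add no more than 10 points per type, and possibly nothing. The actual size is unknown.

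A reader might go further and infer that the endpoint contradicts the aim, or that the planned safety result is invalid. Neither follows. The whole-stay count is usable as an inclusive total, and no stated number, test or sample size depends on the rule. What is affected is the interpretation of a preliminary safety figure, so the priority is low to moderate.

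**What to change.** In sections 4.e.ii and 4.f, state three lines, for events overall and for each type, with all dosed patients as denominator and an exact (Clopper-Pearson) 95% interval on each:

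1. **Aim 2 frequency:** patients with an event absent at the pre-dose interview and first occurring after the first nitroglycerin dose and before any later impaction drug, sedation or endoscopy.
2. **Post-rescue events:** patients with an event occurring after any of those treatments.
3. **Whole-stay total:** as now planned.

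**Cost.** A few sentences and one table. Pre-dose and post-dose symptoms and medication times are already collected. Event onset time and procedure start time should be added if the Data Collection Form does not already hold them.

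**Downside.** Failures have a shorter period before rescue but stay in the same denominator. A late nitroglycerin effect may fall on the second line, and section 6 itself expects slower absorption by this route than sublingually. The three lines should therefore always be reported together. The change concerns only how events are counted and leaves clinical management as it is.
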